#### 15. STUDY TREATMENT EXPOSURE

The date of first dose will be taken from the LTE Day 1 "On Site Dosing Administration" form, and the date of last dose will be taken from the LTE "End of Study" form. Interruptions, compliance, and dose changes are not taken into account for duration of exposure. Study duration and treatment duration will be summarized as continuous variables for each treatment as denoted in the Presentation of Treatment Groups in Appendix 1 using descriptive statistics. The duration of treatment will also be summarized categorically:  $\leq 4$ ,  $\geq 4-8$ ,  $\geq 8-12$ ,  $\geq 12-20$ ,  $\geq 20-28$ ,  $\geq 28-36$ ,  $\geq 36-44$ , and  $\geq 44$  weeks. Additionally, the total subject-years of exposure and subject-years on study will be included in the summary.

Number of tablets taken, missed, and frequency and percentage of subjects who missed at least one dose or who had at least one dose interruptions recorded on the Dosing Administration eCRF will also be summarized. Treatment compliance will also be summarized using both descriptive statistics and summarized categorically: < 85%,  $\ge 85$  to  $\le 115\%$ , and > 115%.

#### 15.1. DERIVATIONS

- Study Duration (days) = date of last study visit date of LTE Day 1 visit + 1
- Treatment duration (days) = date of last LTE study treatment administration date of first LTE study treatment administration + 1
- Treatment duration (weeks) = (date of last LTE study treatment administration date of first LTE study treatment administration + 1)/7.
- Total subject-years on study = sum of duration of time on study across all subjects divided by 365.25
- Total subject-years of exposure = sum of duration of treatment exposure across all subjects divided by 365.25

#### 16. STUDY TREATMENT COMPLIANCE

Compliance with study treatment will be summarized for the Safety Set. Total number of tablets expected, total number of tablets taken, total number of tablets missed, overall compliance with study treatment, frequency and percentage with overall compliance with the following categories: <85%,  $\ge85\%$  to  $\le115\%$ , and >115%. By-visit compliance will also be summarized.

Subjects with administration compliance greater than 115% and subjects who do not return any study treatment or study packaging will be asked for the reason for the overcompliance or missing study treatment. Their responses will be recorded on the Drug Accountability eCRF and will be listed.

#### 16.1. DERIVATIONS

Compliance to study treatment is based on the Drug Accountability eCRF and will be calculated as the number of capsules/tablets taken (total dispensed – total returned) divided by the prescribed number of capsules/tablets, expressed as a percentage (see calculations below).

The study treatment is given three times daily (tid), and it is assumed that the subject should take study treatment from the morning of the visit day at which their treatment is initially dispensed to the evening before their last treatment return date, as subjects are advised to wait to take their dose at the study site until all assessments and procedures have been completed on study days. For example, if the initial dispensation date is Day 1 and the last return date is Day 387, then the subject should have taken 3 capsules/tablets each day on

Days 1 to 386; hence, the total number of prescribed capsules would be  $386 \times 3 = 1,158$ . Multiple bottles may be dispensed at one visit; in these cases, "Per Visit" compliance will be non-missing if at least one bottle is returned.

• "Per Visit" Compliance to study treatment at Visit X will be calculated as follows:

```
\frac{([\text{N of Tablets dispensed at Visit }(X)] - [\text{N of Tablets returned at Visit }(X+1)])}{\{[\text{Date of Visit }(X+1)] - [\text{Date of Dispensing at Visit }(X)]\} \times 3} \times 100
```

• Overall Compliance to study treatment will be calculated as follows:

```
{([N of Tablets dispensed at Visit 1] - [N of Tablets returned at Visit 2])
+ ···+

([N of Tablets dispensed at Visit (X-1)] - [N of Tablets returned at Visit X])}

[Date of Visit X] - [Date of Dispensing at Visit 1] ×3
```

For subjects who permanently stop the study treatment before Week 52, the "Date of Visit X" in Overall Compliance calculations will be replaced by the date of study withdrawal.

#### 17. EFFICACY OUTCOMES

#### 17.1. PRIMARY EFFICACY

Not applicable. No primary efficacy analysis was conducted for the LTE.

[figure not shown]
### 17.2. SECONDARY EFFICACY

Not applicable. No secondary efficacy analysis was conducted for the LTE.

#### 17.3. EXPLORATORY EFFICACY

[figure not shown]

Page 25 of 50

[figure not shown]
Page 26 of 50

Page 27 of 50

[figure not shown]
Page 28 of 50

[figure not shown]
Page 29 of 50

Page 30 of 50

Page 31 of 50

# 18. SAFETY OUTCOMES

All analyses for safety outcomes will be based on the safety analysis set. All safety data will be listed and summarized by actual treatment group. There will be no statistical comparisons

between the treatments for safety data, unless otherwise specified. Unless otherwise stated, exhibits will be displayed by treatment as denoted in the Presentation of Treatment Groups in Appendix 1.

## 18.1. ADVERSE EVENTS

AEs will be coded using MedDRA central coding dictionary, Version 23.0 or higher. New treatment-emergent adverse events (TEAEs) in LTE are defined as:

- An AE that occurs after the first dose of LTE study treatment that was not present before the dosing, OR
- An AE that increases in severity after the first dose of LTE study treatment if the event was present before the dosing treatment.

All TEAEs will be coded and summarized by system organ class (SOC) and preferred term (PT) and will be presented by descending order of frequency. AEs occurring before the first dose of study treatment will be summarized separately from new TEAEs occurring in the LTE. Listings will include all AEs (TEAEs and Non-TEAEs).

See Appendix 2. Partial Date Conventions for handling of partial dates for AEs for the purpose of assigning treatment-emergent flags. In the case where it is not possible to define an AE as treatment-emergent or not, the AE will be classified by the worst case, i.e. treatment emergent.

### **18.1.1. ALL TEAES**

All TEAEs will be summarized by SOC and PT and by treatment as denoted in the Presentation of Treatment Groups in Appendix 1 and presented by descending order of frequency in any treatment. TEAEs will also be summarized by maximum severity and relationship to study treatment. A separate summary of related TEAEs and related TEAEs by maximum severity will also be provided.

#### **18.1.2. SEVERITY**

Severity is classified by grade using the Common Terminology Criteria for Adverse Events version 5.0 (CTCAE v5.0) system as defined below. The CTCAE grade will be assessed by a nurse and/or physician and will be recorded in the AE severity Section on the Adverse Events eCRF.

**Grade 1:** Mild; asymptomatic or mild symptoms; clinical or diagnostic observations only; intervention not indicated.

**Grade 2:** Moderate; minimal, local or noninvasive intervention indicated; limiting age-appropriate instrumental activities of daily living.

**Grade 3:** Severe or medically significant but not immediately life-threatening; hospitalization or prolongation of hospitalization indicated; disabling, limiting self-care activities of daily living (e.g., preparing meals, shopping for groceries or clothes, using the telephone, managing money).

**Grade 4:** Life-threatening consequences, urgent intervention indicated.

**Grade 5:** Death related to AE.

TEAEs with a missing severity but identified as a life-threatening serious adverse event (SAE) or one requiring initial or prolonged hospitalization will be classified as Grade 4 (Potentially Life-threatening), otherwise missing severity will be classified as Grade 3 (severe). If a subject reports a TEAE more than once within that SOC/ PT, the AE with the greatest severity will be used in the corresponding severity summaries.

### 18.1.3. RELATIONSHIP TO STUDY TREATMENT

Relationship is classed as "not related", "unlikely related", "probably related", or "related" (increasing severity of relationship) by the Investigator. A "related" TEAE for the purpose of TEAE summaries is defined as a TEAE with a relationship to study treatment as "related" or "probably related" to study treatment. TEAEs with a missing relationship to study treatment will be regarded as "related" to study treatment. "Unlikely related" will be counted as non-related TEAE. If a subject reports the same AE more than once within the same SOC/PT, the AE with the strictest causality will be used in the corresponding relationship summaries. All TEAEs will be summarized by SOC, PT, and relationship to study treatment.

#### 18.1.4. TEAES LEADING TO DISCONTINUATION OF STUDY TREATMENT

TEAEs leading to permanent discontinuation of study treatment will be identified by action taken being recorded as "Drug withdrawal" on the AE page of the eCRF. All TEAEs leading to discontinuation of study treatment will be summarized by SOC and PT. A listing of all TEAEs leading to discontinuation of study treatment will also be presented.

#### 18.1.5. TEAES LEADING TO STUDY DISCONTINUATION

TEAEs leading to study discontinuation will be noted on the End of Study eCRF. All TEAEs

leading to study discontinuation will be summarized by SOC and PT.

### 18.1.6. SERIOUS AND NON-SERIOUS TEAES

Serious adverse events (SAEs) are those events recorded as "Serious" on the Adverse Events page of the eCRF. All serious TEAEs will be summarized by SOC and PT. All non-serious TEAEs will also be summarized by SOC and PT. A serious AE listing will also be presented.

#### 18.1.7. TEAES LEADING TO DEATH

TEAEs leading to Death are those events which are recorded as "Fatal" on the Adverse Events page of the eCRF. A summary of TEAEs leading to death by SOC and PT will be prepared by treatment.

#### 18.1.8. TEAES OF SPECIAL INTEREST

To date, no AEs of special interest have been identified related to olorinab. Potential AEs of special interest may be identified by clinical or medical reviewers. In addition to appropriate reporting of these events as an AE or SAE, supplementary detailed information may be collected. Any identified AEs of special interest will be summarized by SOC and PT separately. A listing will also be provided.

### 18.1.9. OVERALL SUMMARY OF ADVERSE EVENTS

In addition to the summaries by SOC and PT as described in Sections 18.1.1 to 18.1.5, an overview of TEAEs will be summarized (not broken down by SOC or PT) by number and frequency of subjects and by number of AEs by treatment:

- Any AE (including non-TEAEs)
- Any TEAE
- Any related TEAE
- TEAEs by maximum severity
- Related TEAEs by maximum severity
- TEAEs by relationship to study treatment
- TEAEs leading to study treatment discontinuation
- TEAEs leading to study treatment interruption
- TEAEs leading to study discontinuation
- Related TEAEs leading to study treatment discontinuation
- Related TEAEs leading to study treatment interruption

• Related TEAEs leading to study discontinuation

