#### 3. STUDY OBJECTIVES

#### 3.1. PRIMARY OBJECTIVES

The primary objective is:

• To evaluate the safety and tolerability of long-term administration of olorinab in subjects with irritable bowel syndrome (IBS)

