### 4. STUDY DESIGN

#### 4.1. GENERAL DESCRIPTION

The LTE is an optional extension period that is designed to assess the safety, tolerability, population PK (Ctrough), and efficacy of long-term administration of olorinab in subjects who have completed the Main Study. The LTE will be conducted at the same study sites as the Main Study. Subjects who participate in the LTE will be subjects who complete LTE Visit 2 < 28 days after their Main Study Week 12 visit ("Continuing subjects") or subjects who complete their Main Study Week 12 visit ≥ 28 days prior to LTE Visit 2 ("Gap subjects"). Gap subjects will be required to have an LTE Screening visit approximately 14 days prior to randomization in the LTE. After completing eligibility assessments, subjects will enter a randomized LTE Treatment Period (52 weeks), and a post treatment LTE Follow-Up Period (2 weeks).

Gap subjects who are interested in participating in the LTE must enroll in the LTE within 8 weeks after the IRB approval date of Amendment 3.0. All subjects who meet LTE eligibility criteria will be assigned to olorinab treatment as follows:

- Subjects who received 25 mg or 50 mg olorinab during the Main Study will continue to receive the same dose.
- Subjects who received placebo or 10 mg olorinab during the Main Study will be rerandomized (1:1) in a double-blind manner to receive either 25 mg or 50 mg olorinab.

Subjects who participate in the LTE will include study subjects who completed the Main Study Treatment Period and who meet the applicable inclusion and exclusion criteria for the LTE. Subject enrollment in the LTE will not be capped.

[figure not shown]

Figure 1: Schematic Diagram of Long-Term Extension Design

Abbreviations: AAPS = average abdominal pain score; LTE = long-term extension; tid = 3 times per day; Wk = week

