#### 4.3. CHANGES TO ANALYSIS FROM PROTOCOL

After completing the analysis for the Main Study Period, the decision was made to terminate the study early and end the LTE for all subjects. Analyses for the LTE will reflect all data collected until the study is terminated. Population PK endpoints, Ctrough of olorinab and its primary metabolites, will not be included in this SAP. Removal of PK exhibits (TFLs) was agreed upon on 01APR2021.

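### The LTE adverse-event tables have no time-at-risk measure although the LTE was stopped early, so their crude percentages tend to understate 52-week risk by an unknown amount

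*SAP*

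**What the plan says.** **Design.** Section 3.1 of the LTE SAP gives a single primary objective: safety and tolerability of olorinab given long term. Under Section 4.1, "subjects will enter a randomized LTE Treatment Period (52 weeks), and a post treatment LTE Follow-Up Period". Entry is staggered: continuing subjects move over less than 28 days after their own Main Study Week 12 visit, and gap subjects enrol within 8 weeks of IRB approval of Amendment 3.0.

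**Early stop.** The LTE SAP is dated 17 May 2021. Its Section 4.3 reports that after the Main Study analysis "the decision was made to terminate the study early and end the LTE for all subjects", and adds: "Analyses for the LTE will reflect all data collected until the study is terminated". The only other change listed there is removal of the PK outputs.

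**Adverse events.** Sections 18.1 to 18.1.8 summarise TEAEs by system organ class and preferred term, severity, relationship, seriousness and discontinuation. Section 18.1.9 says "an overview of TEAEs will be summarized (not broken down by SOC or PT) by number and frequency of subjects", and also by number of AEs, by treatment. Protocol Section 8.3.6 carries the Main Study safety methods over to the LTE, and Section 8.3.4.1 defines those as the proportion of subjects with TEAEs.

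**Exposure.** In Section 15, "The duration of treatment will also be summarized categorically", in bins running from up to 4 weeks to 44 weeks or more, and "the total subject-years of exposure and subject-years on study will be included in the summary". Section 15.1 defines: "Total subject-years of exposure = sum of duration of treatment exposure across all subjects divided by 365.25". Nothing legible carries this person-time into an adverse-event table.

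**The concern.** The proportion of subjects with an event depends on how long they were watched. If all had been followed for 52 weeks, the crude percentage would estimate 52-week risk directly. Once subjects enter at different dates and all stop together, it averages over whatever follow-up happened to accrue and refers to no defined period.

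Subjects observed for less than 52 weeks cannot show later events, so the error runs downward. It is greatest for late-onset events, which are what a long-term extension is meant to detect. A reader who takes the table as a one-year safety profile would be reassured too easily on the LTE's only primary objective.

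The SAP was written with the early stop known, and the dates needed for a time-based summary are already used elsewhere in it.

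**Working it through.** **No plan figure to reproduce.** The documents give no LTE sample size, event rate or observed exposure. What follows is illustration under stated assumptions.

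**Inputs from the documents.** Planned treatment of 52 weeks (LTE SAP 4.1); eight duration bins (LTE SAP 15).

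**Assumed inputs.** Bin midpoints of 2, 6, 10, 16, 24, 32, 40 and 48 weeks, with three sets of weights:
- Equal: 1/8 each; mean 178/8 = 22.25 weeks.
- Short-heavy: 0.15, 0.15, 0.15, 0.20, 0.15, 0.10, 0.05, 0.05; mean 17.1 weeks.
- Long-heavy: 0.05, 0.05, 0.05, 0.10, 0.10, 0.15, 0.20, 0.30; mean 32.1 weeks.

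**Formula.** Expected crude proportion = Σ wᵢ F(tᵢ), where F(t) is the risk of a first event by week t and R = F(52).

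**Case 1, constant hazard.** F(t) = 1 − exp(−λt), with λ = −ln(1 − R)/52. For R = 20%, λ = 0.2231/52 = 0.00429 per week. At the midpoints F is 0.85, 2.54, 4.20, 6.64, 9.79, 12.83, 15.77 and 18.61%. The equal-weight result is their sum, 71.23%, divided by 8 = 8.9%.

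**Case 2, early onset.** 80% of the 52-week risk falls evenly in weeks 0 to 4 and the rest evenly in weeks 4 to 52: F(t) = R × [0.8 × min(t,4)/4 + 0.2 × max(0, t − 4)/48]. For R = 20%, F at the midpoints is 8.00, 16.17, 16.50, 17.00, 17.67, 18.33, 19.00 and 19.67%.

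| True 52-week risk 20% | Short-heavy | Equal | Long-heavy |
|---|---|---|---|
| Crude, constant hazard | 6.9% | 8.9% | 12.7% |
| Ratio to true risk | 0.35 | 0.45 | 0.63 |
| Crude, early onset | 15.9% | 16.5% | 18.0% |
| Ratio to true risk | 0.80 | 0.83 | 0.90 |

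Under constant hazard, true risks of 5%, 10% and 40% give crude ranges of 1.7–3.1%, 3.4–6.3% and 14.8–26.2%. Over all four risks the ratio runs from 0.33 to 0.66.

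**Would a rate per subject-year be enough?** Under constant hazard, yes: subjects with a first event divided by time to first event or censoring, converted by 1 − exp(−52 × weekly rate), returns 20.0% for all three mixes. Under early onset, no. Take R = 20% and exposure uniform over 4 to 52 weeks:
- F is linear beyond week 4, so the crude value is F at the mean of 28 weeks: 0.20 × (0.8 + 0.2 × 24/48) = 18.0%.
- Mean time to first event or censoring is 23.52 weeks, so the rate is 0.18/23.52 = 0.00765 per week, about 40 per 100 subject-years (365.25/7 = 52.18 weeks per year).
- Implied 52-week risk: 1 − exp(−52 × 0.00765) = 33%, further from 20% than the crude figure.
- The same process over 12 weeks gives F(12) = 16.67% and a mean time of 10.37 weeks, so 0.1667/10.37 = 0.01607 per week, about 84 per 100 subject-years. Setting the LTE rate beside a 12-week rate would suggest a drop in risk produced only by the length of follow-up.

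**The case against.** The other side has a good case on several points.

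- **The crude percentages are a valid description.** The SAP does not claim that they estimate 52-week risk, and no safety comparison between treatments is planned unless otherwise specified. This stands: the gap is one of estimation and interpretation, not a faulty test.
- **The truncation is disclosed.** A reader might infer that the SAP treats everyone as having had 52 weeks. It does not: Section 4.3 says the analyses reflect data up to termination, and Section 15 tabulates duration and subject-years.
- **Part of the answer can be derived.** AE counts and subject-years are both planned by treatment, so overall AEs per subject-year follow by division. But recurrent events in a few subjects can dominate that figure. First-event incidence cannot be obtained exactly, because the planned subject-years do not stop at the first event.
- **The bins are not data.** A reader might infer from Section 15 that exposure actually ran from under 4 to over 44 weeks. Those are display categories; observed exposure is not reported.
- **Unequal exposure across the six treatment sequences is not shown.** Placebo and 10 mg subjects are re-randomised 1:1, and nothing documents a difference in follow-up.
- **Precision may be poor.** LTE size is not fixed. With zero events in an assumed 5 subject-years, the exact upper 95% limit is 3.69/5, about 74 per 100.
- **Absence is not fully verifiable.** Table shells are in a separate file and the appendix on presentation of treatment groups is not legible here.

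These limit the point but leave its core: no legible section of the LTE SAP links adverse events to time at risk.

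**Conclusion.** The point holds as a gap in estimation on the LTE's only primary objective. With staggered entry and a common stop, crude percentages tend to understate 52-week risk, and no other planned output in the legible text supplies the missing measure.

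The size is unknown. It is about one third to two thirds of the true risk under a constant hazard, and 80 to 90% of it when onset is mostly in the first 4 weeks. Both ranges rest on assumed exposure mixes and assumed risks. A reader might want a single figure, such as the table showing about half of the one-year risk; the documents support none.

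Nor is a rate per subject-year a sufficient cure, since with early onset it can mislead more than the crude percentage. Kaplan-Meier cumulative incidence does not need a constant hazard and should lead. It does assume that censoring is unrelated to event risk, which is reasonable for the common stop but less certain for individual withdrawals.

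The change is worth making. It would not invalidate anything already planned.

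**What to change.** Keep the crude counts and percentages. In LTE SAP Section 18.1, for any TEAE, related TEAEs, serious TEAEs, TEAEs leading to discontinuation and the commonest preferred terms, add:

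1. Kaplan-Meier cumulative incidence of first event by LTE dose (25 mg, 50 mg), with numbers at risk and 95% CI.
2. Subjects with a first event per 100 subject-years at risk, with exact Poisson 95% CI, by LTE dose and, descriptively, by the six treatment sequences.
3. A stated at-risk window: first LTE dose to first event or a defined end of AE observation. This must be written down because Section 15.1 ends exposure at last dose, Protocol Section 7.8.2.2 continues AE reporting to 30 days after it, and the LTE TEAE definition in Section 18.1 gives no end.
4. A note that the rate assumes a roughly constant hazard and should not be compared directly with the 12-week Main Study.

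The cost is SAP wording and a few more table columns, from dates the SAP already uses (AE onset, first and last LTE dose, last visit). The drawback is wide intervals in small sequences.

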### **18.2. DEATHS**

For any reports of death during the study as recorded on the End of Study page of the eCRF, the information will be presented in a listing.

### 18.3. LABORATORY EVALUATIONS

Results from the central laboratory will be included in the reporting of this study for chemistry, hematology, coagulation, urinalysis, thyroid chemistry, celiac, and virology. pregnancy. A list of laboratory assessments to be included in the outputs is included in Table 3 in the protocol. If local and central laboratory assessments are available from the same day, central laboratory assessments will be used in the analysis.

Presentations will use SI Units. Quantitative laboratory measurements reported as "< X", i.e. below the lower limit of quantification (BLQ), or "> X", i.e. above the upper limit of quantification (ULQ), will be converted to X for the purpose of quantitative summaries, but will be presented as recorded, i.e. as "< X" or "> X" in the listings.

Laboratory parameters such as hepatic enzymes, renal function and hematology values will be grouped and presented together. The following summaries will be provided for laboratory data:

- Value and change from LTE baseline by visit (for quantitative measurements)
- Incidence of abnormal values according to laboratory reference ranges by visit
- Shift from LTE baseline to end of treatment according to laboratory reference range (for quantitative measurements and categorical measurements)
- Summary of subjects with treatment-emergent abnormal lab results
- Listing of subject's laboratory assessments at all timepoints. Values outside of the central laboratory reference range will be flagged. Values obtained from local laboratory will be flagged.

